8.8 Week 104 (Visit 13) or Early Termination Visit

The following procedures or assessments will be completed:

- Record concomitant medications
- Record AEs
- eC-SSRS
- HADS
- Administer the HAQ-DI
- Administer the SF-36
- Administer the PGADA
- Administer the PtAAP
- Administer the PsAID-9
- Administer the TB questionnaire
- Measure vital signs (temperature, pulse, and BP)
- Measure body weight
- Perform a physical examination, including an evaluation for signs and symptoms of active TB and risk for exposure to TB
- Perform TJC/SJC
- Determine BSA affected by PSO using the BSA palm method
- If the BSA affected by PSO is $\geq 3\%$ at Baseline of PA0008, determine the PASI
- Determine the MASES
- Determine the LDI
- Perform the PhGADA
- Perform an ECG
- Collect samples for hematology/biochemistry
- If there has been a delay in menses, perform a urine pregnancy test
- Collect blood sample for CRP

- Collect blood sample for bimekizumab plasma concentrations and anti bimekizumab antibody detection
- Record visit in the IXRS

8.9 SFU Visit (20 weeks after the final dose of IMP)

The following procedures or assessments will be completed:

- Record concomitant medications
- Record AEs
- eC-SSRS
- Administer the TB questionnaire
- Measure vital signs (temperature, pulse, and BP)
- Measure body weight
- Perform a physical examination, including an evaluation for signs and symptoms of active TB and risk for exposure to TB
- Collect samples for hematology/biochemistry
- If there has been a delay in menses, perform a urine pregnancy test
- Collect blood sample for CRP
- Collect blood sample for bimekizumab plasma concentrations and anti bimekizumab antibody detection
- Perform an IGRA TB test
- Record visit in the IXRS

8.10 Early Termination Visit

Subjects withdrawing early from the study (see [Section 6.3](#)) will undergo the same assessments as the Week 104 Visit (see [Section 8.8](#)) and will enter the SFU Period.

8.11 Unscheduled Visit

At the Investigator's discretion, an Unscheduled Visit may be completed at any time during the study but prior to the SFU Visit, if deemed necessary for the subject's safety and well-being.

If an Unscheduled Visit is conducted due to safety or efficacy reasons, an eC-SSRS assessment will be performed with the subject during the visit. If an Unscheduled Visit is conducted for reasons other than safety or efficacy concerns (eg, replacement of lost medication, repeated collection of a laboratory specimen due to collection or analysis issues) an eC-SSRS will not be required at these visits.

At this visit, any of the following assessments may be performed, depending on the reason for the visit:

- Record concomitant medication
- Record AEs
- eC-SSRS
- Measure vital signs (temperature, pulse, and BP)
- Physical examination
- Record 12-lead ECG
- If medically indicated, obtain blood sample(s) for standard safety laboratory tests (hematology, serum chemistry)
- Obtain urine sample for standard safety laboratory tests (including urine pregnancy test in women of childbearing potential).

9 ASSESSMENT OF SAFETY

9.1 Adverse events

9.1.1 Definition of AE

An AE is any untoward medical occurrence in a patient or clinical investigation subject administered a pharmaceutical product that does not necessarily have a causal relationship with this treatment. An AE can therefore be any unfavorable and unintended sign (including an abnormal laboratory finding), symptom, or disease temporally associated with the use of a medicinal (investigational) product, whether or not related to the medicinal (investigational) product.

In order to ensure complete safety data collection, all AEs occurring during the study (ie, after the signing of the ICF), including any pretreatment and posttreatment periods required by the protocol, must be reported in the eCRF even if no IMP was taken but specific study procedures were conducted. This includes all AEs not present prior to the initial visit and all AEs that recurred or worsened after the initial visit.

Signs or symptoms of the condition/disease for which the IMP is being studied should be recorded as AEs only if their nature changes considerably or their frequency or intensity increases in a clinically significant manner as compared to the clinical profile known to the investigator from the subject's history or study entry.

Adverse events that occurred during the PA0008 lead-in study and are still deemed ongoing at the time of enrolment (signed ICF) will be captured in the database and followed up, as described in [Section 9.1.6](#).

9.1.2 AEs of special interest

An AE of special interest (AESI) is any AE that a regulatory authority has mandated be reported on an expedited basis, regardless of the seriousness, expectedness, or relatedness of the AE to the administration of a UCB product/compound.

Potential Hy's Law, defined as $\geq 3 \times \text{ULN}$ ALT or AST with coexisting $\geq 2 \times \text{ULN}$ total bilirubin in the absence of $\geq 2 \times \text{ULN}$ alkaline phosphatase (ALP), with no alternative explanation for the biochemical abnormality, must ALWAYS be reported to UCB as an AESI (ie, without waiting for any additional etiologic investigations to have been concluded). Follow-up information should then be reported if an alternative etiology is identified during investigation and monitoring of the subject.

9.1.3 Other safety topics of interest

Pre-specified safety topics of interest for the study are: infections (serious, opportunistic, fungal and TB), neutropenia, hypersensitivity, suicidal ideation and behavior, depression, major cardiovascular events, liver function test changes/enzyme elevations, malignancies, and inflammatory bowel diseases (with gastroenterology referral, as appropriate). This is based on findings from the IMP clinical program to date, potential risks generally associated with biologic immunomodulators, or findings from other medicines with a related mechanism of action. There are no specific AE reporting requirements for these topics, however special monitoring, additional data collection activities, and/or enhanced signal detection activities (within UCB) are in place.

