9. Subject develops laboratory abnormalities (with or without clinical symptoms) of alanine aminotransferase (ALT) or aspartate aminotransferase (AST) as defined in [Section 6.3.1](#); neutrophils $<0.5 \times 10^9/L$ (neutropenia); lymphocytes $<0.5 \times 10^9/L$ (lymphopenia). Any laboratory value or change judged to be clinically significant by the Investigator should prompt consideration of whether the subject should continue on the investigational medicinal product (IMP). For clarification, laboratory values that are markedly abnormal as per [Table 17-1](#) and [Table 17-2](#) will be flagged to the Investigator and to the medical monitor but do not trigger mandatory withdrawal unless listed above. (Refer to [Section 6.3.1](#) for withdrawal criteria in relation to potential drug-induced liver injury [PDILI].)
10. Subject has active suicidal ideation as indicated by a positive response (“Yes”) to Questions 4 or 5 or to the suicidal behavior questions of the “Since Last Visit” version of the self-rated electronic Columbia-Suicide Severity Rating Scale (eC-SSRS). The subject should be referred immediately to a Mental Healthcare Professional and must be withdrawn from the study.
11. Subjects with a HADS-D score ≥ 15 must be withdrawn. Any subject who develops a HADS-D score of >10 during the study should be referred immediately to a Mental Healthcare Professional for further evaluation and potential withdrawal by the Investigator.
12. Subjects with newly diagnosed inflammatory bowel disease (IBD) or with IBD flares during the study must:
 - Be referred, as appropriate, to a health care professional treating IBD, such as a gastroenterologist
 - Discontinue IMP and be followed-up until resolution of active IBD symptoms

If IBD flares increase in severity or frequency during the study, the Investigator should use clinical judgment in deciding whether the subject should continue in the study and contact the Medical Monitor and UCB study physician to confirm the subject's suitability for continued participation in the study.

All subjects who withdraw from the study due to an AE must be followed until resolution of the event or until the event is considered stable. All subjects who withdraw from the study due to development of a laboratory abnormality must be closely monitored.

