### 10.2.3 Adverse events of special interest and safety topics of interest

AESI (in the opinion of the investigator) will be flagged in the study database. In addition, an AESI is considered to have occurred if any TEAE which meets the Hy's Law criteria, defined as  $\geq 3x$  upper limit of normal (ULN) alanine aminotransferase (ALT) or aspartate aminotransferase (AST) with coexisting  $\geq 2x$ ULN total bilirubin in the absence of  $\geq 2x$ ULN alkaline phosphatase (ALP), with no alternative explanation for the biochemical abnormality. Hy's law criteria will be summarized as described in Section 10.3.

TEAEs are defined as Safety Topics of Interest and reported as follows:

1. Infections (serious, opportunistic, fungal and TB)

- Serious infections will be identified based on MedDRA classification (SOC “Infections and infestations”). (Although not required by the ‘Safety Topics of Interest for the Bimekizumab Program’ document, a separate table will be created for these events.)
- Fungal infections will be summarized in a stand-alone table. The table will include all TEAEs (serious and non-serious) which code into the High Level Group Term “Fungal infectious disorders”.
- Opportunistic infections (including TB) will be summarized in a stand-alone table. The table will include all opportunistic infection TEAEs identified using UCB-defined search criteria which were adjudicated as opportunistic infections. The process for identifying opportunistic infections is outlined in [Section 12.4](#).

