#### 5. Suicidal Ideation and Behavior

An external neuropsychiatric adjudication committee will evaluate potential neuropsychiatric events and determine whether any of those events were associated with suicidal ideation and behavior (SIB). A table and listing for SIB events as determined by the adjudication committee will be produced.

Additionally, a listing of all events identified for potential review by the neuropsychiatric adjudication committee will be produced. This listing will indicate whether each event was escalated to the committee for formal review/adjudication. A separate listing will also be produced to summarize the adjudicated results of all events escalated to the full committee.

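### Depression is a protocol safety topic with no counterpart in the SAP, so neither a grouped depression rate nor a count at the HADS-D action levels is planned

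*Protocol*

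**What the plan says.** Protocol 9.1.3 gives nine pre-specified safety topics, and the run "neutropenia, hypersensitivity, suicidal ideation and behavior, depression, major cardiovascular events" shows depression listed separately from suicidal ideation and behavior (SIB). Protocol 6.3, criterion 11, attaches two actions to the HADS depression score: "Subjects with a HADS-D score ≥ 15 must be withdrawn" and "Any subject who develops a HADS-D score of >10 during the study should be referred immediately to a Mental Healthcare Professional".

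SAP 10.2.3 introduces its list with "TEAEs are defined as Safety Topics of Interest and reported as follows" and then numbers eight topics. Topic 5 is the closest to depression. There an external neuropsychiatric committee is to "determine whether any of those events were associated with suicidal ideation and behavior", and "A table and listing for SIB events as determined by the adjudication committee will be produced". The end of SAP 10.2.3 gives every listed topic incidence by MedDRA level, an EAIR with 95% CI and an EAER.

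HADS is handled as an efficacy variable. SAP 8.3 summarizes the change in HADS-A and HADS-D by visit, and the proportion of subjects with both scores below 8. Both use the FAS after multiple imputation (SAP 4.2.1 and Table 4-2).

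**The concern.** Long-term safety is the primary objective, and the study has a single treatment arm. An exposure-adjusted rate for a defined group of terms is what allows a topic to be set against other data. The SAP provides this for eight topics, neutropenia for example being grouped from nine preferred terms, but not for depression.

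The same gap appears on the scale side. HADS-D is both an outcome and a trigger for referral or withdrawal, yet no planned table shows how many subjects reached either level. A reader of the study report would have to assemble both results from listings, after the data are known and without a pre-specified definition.

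**Working it through.** No figure in the plan needs reproducing. The check is a comparison of passages, followed by an illustration of scale.

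**1. Topics, protocol 9.1.3 against SAP 10.2.3**

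| Protocol topic | SAP topic |
|---|---|
| Infections | 1 |
| Malignancies | 2 |
| Major cardiovascular events | 3 (MACE) |
| Neutropenia | 4 |
| Suicidal ideation and behavior | 5 |
| Inflammatory bowel disease | 6 |
| Hypersensitivity | 7 |
| Liver changes | 8 |
| Depression | none |

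Nine topics against eight; only depression is unmatched. The topic listings in SAP 10.2 have no depression entry either. SAP 3.10 reports smaller changes, such as replacing ACR20 by ACR50 in a figure, but not this one.

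**2. Where depression can still be read**

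- SAP 10.2 tabulates all TEAEs and serious TEAEs by SOC, HLT and PT with EAIR and EAER; SAP 10 and 10.2.2 supply the 95% CI. A depression preferred term therefore has its own row and rate.
- SAP 10.2.2 computes the EAIR at each coding level from the first event at that level, so SOC and HLT rows are proper grouped rates. The SOC row is too broad for this purpose: protocol Table 9-1 places anxiety and depression in the same SOC. The documents do not say whether all relevant terms share one HLT.
- Events identified for, or escalated to, the neuropsychiatric committee are listed (SAP 10.2 and topic 5). Only the committee table and the SIB listing are confined to SIB.

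**3. Protocol 6.3 triggers and what the SAP tabulates**

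| Trigger | SAP summary |
|---|---|
| ALT/AST multiples of ULN | yes, 10.3 |
| Neutrophils <0.5 | yes, Table 10-9, Grade 4 |
| Lymphocytes <0.5 | yes, Table 10-7 |
| eC-SSRS ideation or behavior | yes, 10.5.3 (incidence) |
| HADS-D >10 | no |
| HADS-D ≥15 | no |

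The joint category (HADS-D <8 and HADS-A <8) cannot stand in for these counts. A subject outside it may have a raised anxiety score only. It is also built from imputed values under a missing-at-random assumption, so a subject withdrawn for a high HADS-D contributes imputed scores at later visits.

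**4. Scale (illustrative)**

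Inputs: up to 200 subjects (protocol 5.1.3); last dose at Week 100, which is 700 days; 140 days of follow-up at risk (SAP Table 10-2).

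- Maximum time at risk: 200 × (700 + 140) / 365.25 = 460 patient-years.
- With n subjects affected, the rate is about 100 × n / 460, with the exact Poisson interval of SAP 10.2.2.
- n = 5: 1.09 per 100 patient-years (0.35 to 2.54).
- n = 10: 2.17 per 100 patient-years (1.04 to 4.00).

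The counts of five and ten are assumptions. Dividing by 460 only approximates the SAP's EAIR, which stops time at first onset. In the extreme case that every onset is on day 1, the denominators fall to about 195 × 840 / 365.25 = 448 and 190 × 840 / 365.25 = 437. The rates then rise to about 1.11 and 2.29, so the approximation is close.

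**5. Why rows cannot simply be added**

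Suppose two depression rows in different HLTs show 5 and 10 subjects. Between 10 and 15 distinct subjects are then affected, depending on overlap. The grouped rate lies between roughly 10/460 = 2.17 and 15/460 = 3.26 per 100 patient-years, and the tables cannot say where.

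**The case against.** The strongest reply is that nothing is hidden. A reader might infer from the missing topic that no depression rate will be reported, or that the neuropsychiatric committee output is limited to SIB. The documents support neither reading: the general TEAE tables carry rates at three coding levels, and the committee listings cover all events identified or escalated. Individual HADS data and derived scores are listed for the FAS (SAP 8), and TEAEs leading to discontinuation are tabulated by PT. A grouped rate could be derived by hand from the AE and exposure listings. All of this stands, and it limits the point to the absence of a pre-defined grouped rate and of threshold counts.

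A reader might also infer that the SAP departs from a protocol-defined analysis. That is not supported. Protocol 13.3.1 asks for no topic-level table on any topic. Protocol 4.3.2 lists HADS under efficacy, with change and normal status only. Protocol 9.1.3 adds "There are no specific AE reporting requirements for these topics". That sentence, however, applies equally to the eight topics the SAP does tabulate, so it does not explain why one was left out.

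The SAP also refers to a programme-level document on safety topics that cannot be seen here. Whether the omission was deliberate therefore cannot be judged.

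**Conclusion.** The point holds as a gap in alignment and completeness, worth correcting before database lock. It does not undermine the primary analysis. Depression is the only protocol safety topic without a SAP definition, and neither of the two HADS-D action levels is counted. The consequence is that depression must be read term by term, or rebuilt from listings after the event.

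The rates of about 1.1 and 2.2 per 100 patient-years indicate only the order of magnitude such a table might show. They rest on assumed counts, full enrolment and complete follow-up. If the relevant terms all fall in one HLT that contains little else, that row would come close to the missing rate; the documents do not settle this.

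**What to change.** 1. Add depression to SAP 10.2.3 as a ninth topic, with a named MedDRA search chosen by the safety team and fixed before database lock. Report incidence, EAIR with 95% CI, EAER and a listing, as for the other topics.
2. Add one table for the Safety Set on observed data: number and percentage of subjects with HADS-D >10 and with HADS-D ≥15 at any post-entry visit, shown by whether that level was already present at PA0009 entry. The cut-offs are those already in protocol 6.3; no clinical rule changes.
3. If the topic is left out on purpose, say so and justify it in SAP 3.10.

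The cost is one topic table and listing, one threshold table and the SAP wording. The data are already collected and the formats exist.

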9.1.4 Procedures for reporting and recording AEs

The subject will be given the opportunity to report AEs spontaneously. A general prompt will also be given at each study visit to detect AEs. For example:

“Did you notice anything unusual about your health (since your last visit)?”

In addition, the Investigator should review any self-assessment procedures (eg, diary cards) employed in the study.

9.1.5 Description of AEs

When recording an AE, the Investigator should use the overall diagnosis or syndrome using standard medical terminology, rather than recording individual symptoms or signs. The eCRF and source documents should be consistent. Any discrepancies between the subject's own words on his/her own records (eg, diary card) and the corresponding medical terminology should be clarified in the source documentation.

When recording the intensity of an AE in the CRF (ie, mild, moderate, or severe), the Investigator should use the following criteria:

- Mild: the subject is aware of the sign or symptom (syndrome), but it does not interfere with his/her usual activities and/or is of no clinical consequence
- Moderate: the AE interferes with the usual activities of the subject or it is of some clinical consequence
- Severe: the subject is unable to work normally or to carry out his/her usual activities, or the AE is of definite clinical consequence

Details for completion of the AE eCRF (including judgment of intensity and relationship to IMP) are described in the eCRF Completion Guidelines.

9.1.6 Follow-up of AEs

An AE should be followed until it has resolved, has a stable sequelae, the Investigator determines that it is no longer clinically significant, or the subject is lost to follow-up. This follow-up requirement applies to AEs, SAEs, AESIs, and other safety topics of interest; further details regarding follow-up of PDILI events are provided in [Section 9.5.1.5](#). Information on SAEs obtained after clinical database lock will be captured through the Patient Safety (PS) database without limitation of time.

If an AE is ongoing at the end of the study for a subject, follow-up should be provided until resolution/stable level of sequelae is achieved, or until the Investigator no longer deems that it is clinically significant, or until the subject is lost to follow-up. If no follow-up is provided, the Investigator must provide a justification. The follow-up will usually be continued for 20 weeks after the subject has discontinued his/her IMP.

9.1.7 Rule for repetition of an AE

An increase in the intensity of an AE should lead to the repetition of the AE being reported with:

- The outcome date of the first AE that is not related to the natural course of the disease being the same as the start date of the repeated AE, and the outcome of “worsening”
- The AE verbatim term being the same for the first and repeated AE, so that the repeated AE can be easily identified as the worsening of the first one

9.1.8 Pregnancy

If an Investigator is notified that a subject has become pregnant after the first intake of any IMP, the Investigator must immediately notify UCB’s PS department by providing the completed Pregnancy Report and Outcome Form (for contact details see SAE reporting information at the beginning of this protocol). The subject should be withdrawn from the study as soon as pregnancy is known (by positive pregnancy test), and the following should be completed:

- The subject should return for the ET Visit.
- The subject should immediately stop the intake of the IMP.
- An SFU Visit should be scheduled 20 weeks after the subject has discontinued her IMP.

The Investigator must inform the subject of information currently known about potential risks and about available treatment alternatives.

The pregnancy will be documented on the Pregnancy Report and Outcome Form provided to the Investigator. The progression of the pregnancy and the eventual birth (if applicable) must be followed up using the Pregnancy Report and Outcome Form in which the Investigator has to report on the health of the mother and of the child. Every reasonable attempt should be made to follow the health of the child for 30 days after birth for any significant medical issues. In certain circumstances, UCB may request that follow-up is continued for a period longer than 30 days. If the subject is lost to follow-up and/or refuses to give information, written documentation of attempts to contact the subject needs to be provided by the Investigator and filed at the site. UCB’s PS department is the primary contact for any questions related to the data collection for the pregnancy, eventual birth, and follow-up.

In cases where the partner of a male subject enrolled in a clinical study becomes pregnant, the Investigator or designee is asked to contact the subject to request consent of the partner via the Partner Pregnancy Consent Form that has been approved by the responsible IRB/IEC and should be available in the Investigator site file. In case of questions about the consent process, the Investigator may contact the UCB/Contract Research Organization (CRO) contract monitor for the study. The Investigator will complete the Pregnancy Report and Outcome Form and send it to UCB's PS department (for contact details see SAE reporting information at the beginning of this protocol) only after the partner has agreed that additional information can be captured and has provided the signed Partner Pregnancy Consent Form. UCB's PS department is also the primary contact for any questions related to the data collection for the partner pregnancy, eventual birth, and follow-up.

A pregnancy becomes an SAE in the following circumstances: miscarriage, elective abortion when medically indicated (e.g. when pregnancy is endangering life or health of woman or when fetus will be born with severe abnormalities), unintended pregnancy after hormonal contraceptive failure (if the hormonal contraceptive was correctly used), ectopic pregnancy, fetal demise, or any congenital anomaly/birth defect of the baby. Those SAEs must be additionally reported using the Investigator SAE Report form.

